# 17.5 King's Brief Interstitial Lung Disease Questionnaire

### The King's Brief Interstitial Lung Disease Questionnaire (K-BILD)©2011

This questionnaire is designed to assess the impact of your lung disease on various aspects of your life. Please circle the response that best applies to you for each question

	The state of the s					
		s climbing stairs or walking				
Every time	2. Most times	3. Several Times	4. Some times	5. Occasionally	6. Rarely	7. Never
2. In the last 2 weeks	, because of my lung c	ondition, my chest has felt	tight.			
1. All of the time	

Most of the time

	3. A good bit of the time	4. Some of the time	5. A little of the time	6. Hardly any of the time	7. None of the time
3. In the last 2 weeks	have you worried abou	at the seriousness of your la	ung complaint?			
1. All of the time	2. Most of the time	3. A good bit of the time	4. Some of the time	5. A little of the time	6. Hardly any of the time	7. None of the time
4. In the last 2 weeks	have you avoided doin	g things that make you brea	athless?			
1. All of the time	2. Most of the time	3. A good bit of the time	4. Some of the time	5. A little of the time	6. Hardly any of the time	7. None of the time
5. In the last 2 weeks	have you felt in contro	of your lung condition?				
1. None of the time	2. Hardly any of the tin	ne 3. A little of the time	4. Some of the time	5. A good bit of the time	6. Most of the time	7. All of the time
6. In the last 2 weeks	, has your lung complai	int made you feel fed up or	down in the dumps?			
1. All of the time	2. Most of the time	3. A good bit of the time	4. Some of the time	5. A little of the time	6. Hardly any of the time	7. None of the time
7. In the last 2 weeks	, I have felt the urge to	breathe, also known as 'ai	r hunger'.			
1. All of the time	2. Most of the time	3. A good bit of the time	4. Some of the time	5. A little of the time	6. Hardly any of the time	7. None of the time
8. In the last 2 weeks	, my lung condition has	made me feel anxious.				
1. All of the time	2. Most of the time	3. A good bit of the time	4. Some of the time	5. A little of the time	6. Hardly any of the time	7. None of the time
9. In the last 2 weeks	, how often have you e	xperienced 'wheeze' or whi	istling sounds from you	r chest?		
1. All of the time	2. Most of the time	3. A good bit of the time	4. Some of the time	5. A little of the time	6. Hardly any of the time	7. None of the time
10. In the last 2 weel	s, how much of the tim	e have you felt your lung d	isease is getting worse	?	10 10	
1. All of the time	2. Most of the time	3. A good bit of the time	4. Some of the time	5. A little of the time	6. Hardly any of the time	7. None of the time
11. In the last 2 weel	s has your lung conditi	on interfered with your job	or other daily tasks?			
1. All of the time	2. Most of the time	3. A good bit of the time	4. Some of the time	5. A little of the time	6. Hardly any of the time	7. None of the time
12. In the last 2 weel	s have you expected yo	our lung complaint to get w	orse?			
1. All of the time	2. Most of the time	3. A good bit of the time	4. Some of the time	5. A little of the time	6. Hardly any of the time	7. None of the time
13. In the last 2 week	s, how much has your	lung condition limited you c	arrying things, for exam	nple, groceries?		
1. All of the time	2. Most of the time	3. A good bit of the time	4. Some of the time	5. A little of the time	6. Hardly any of the time	7. None of the time
14. In the last 2 week	s, has your lung condit	ion made you think more ab	out the end of your life	?		
1. All of the time	2. Most of the time	3. A good bit of the time		5. A little of the time	6. Hardly any of the time	7. None of the time
15. Are you financially	worse off because of					
1. A significant amount		3. A considerable amount	4.A reasonable amount	5. A small amount	6. Hardly at all	7. Not at all

Source: [Patel et al., 2012]

Fipaxalparant (HZN-825)

# 17.6 Leicester Cough Questionnaire

I. In the last 2 wee	ks, have you had ch	est or stomach pains	s as a result of your	cough?		
1 All of the time	2 Most of the time	3 A good bit of the time	4 Some of the time	5 A little of the time	6 Hardly any of the time	7 None of the tin
		othered by sputum (			, 1010, 011, 011110	
1	2 Most times	3 Several times	4 Some times	5	6 Rarely	7 Never
Every time  In the last 2 wee		red because of your		Occasionally	Korely	rvever
1	2	3	4	5	6	7
All of the time	Most of the time	A good bit of the time	Some of the time	A little of the time	Hardly any of the time	None of the tin

 
In the last 2 wee
 
	ks, have you telt in a	ontrol of your cough	4	5	6	7
None of the time	Hardly any of the time	A little of the time	Some of the time	A good bit of the time	Most of the time	All of the time
i. How often during	g the last 2 weeks he	ove you felt embarra	ssed by your cough	ing?	4	7
All of the time	Most of the time	A good bit of the time	Some of the time	A little of the time	Hardly any of the time	None of the tin
. In the last 2 wee	ks, my cough has m	ade me feel anxious				
1 All of the time	2 Most of the time	3 A good bit of the time	4 Some of the time	5 A little of the time	6 Hardly any of the time	7 None of the tin
7. In the last 2 wee	ks, my cough has in	terfered with my job,	or other daily tasks	5		
1 All of the time	2 Most of the time	3 A good bit of the time	4 Some of the time	5 A little of the time	6 Hardly any of the time	7 None of the tir
		gh interfered with th			riolog ony of the mile	Traine of the III
1	2	3	4	5	6	7
All of the time	Most of the time	A good bit of the time	Some of the time	A little of the time	Hardly any of the time	None of the tir
In the last 2 wee	ks, exposure to pain 2	ts or fumes has mad	e me cougn 4	5	6	7
All of the time	Most of the time	A good bit of the time	Some of the time	A little of the time	Hardly any of the time	None of the tir
0. In the last 2 we	eks, has your cough	disturbed your sleep	p\$		,	
All of the time	Most of the time	A good bit of the time	Some of the time	A little of the time	6 Hardly any of the time	None of the tir
1. In the last 2 we	eks, how many time	s a day have you ha	d coughing bouts?			
1 All of the time (continuously)	
 
Most times during the day
 
	
 
Several times during the day
 
	4 Some times during the day	5 Occasionally through the day	6 Rarely	7 None
2. In the last 2 we	eks, my cough has r	nade me feel frustra	ted		4	
All of the time	Most of the time	A good bit of the time	Some of the time	A little of the time	Hardly any of the time	None of the tir
3. In the last 2 we	eks, my cough has r	nade me feel fed up				
1 All of the time	2 Most of the time	3 A good bit of the time	4 Some of the time	5 A little of the time	6 Hardly any of the time	7 None of the tir
4. In the last 2 we	eks, have you suffer	ed from a hoarse vo	ice as a result of yo	ur cough?		
1 All of the time	2 Most of the time	3 A good bit of the time	4 Some of the time	5 A little of the time	6 Hardly any of the time	7 None of the tir
	eks, have you had a		Some of the fille	A lime of the lime	ridialy dily of the time	redrie of line in
1	2	3	4	5	6	7
None of the time	Hardly any of the time		Some of the time	A good bit of the time	Most of the time	All of the time
6. In the last 2 we	eks, have you worrie	ed that your cough n	nay indicate serious	illness¥	6	7
All of the time	Most of the time	A good bit of the time	Some of the time	A little of the time	Hardly any of the time	None of the tir
7. In the last 2 we	eks, have you been	concerned that othe	r people think some	thing is wrong with y	ou, because of you	r cough?
All of the time	Most of the time	A good bit of the time	Some of the time	A little of the time	o Hardly any of the time	None of the tir
8. In the last 2 we	eks, my cough has i	nterrupted conversat	tion or telephone co	ills		
1 Every time	2 Most times	3 A good bit of the time	4 Some of the time	5 A little of the time	6 Hardly any of the time	7 None of the tir
					,,	
9. In the last 2 we	eks, I feel that my co	ough has annoved m	ly parmer, lamily or			

# 17.7 SF-12® Health Survey (SF-12)

(A WHOLLY OWNED SUBSIDIARY OF AMGEN INC.)

SF-12v2 TM Health Survey  (SF-12 v2 Standard, US Version 2.0)  To be completed by the PATIENT  Directions: This survey asks for your views about your health. This information will help you keep track of how you feel and how well you are able to do your usual activities. If you need to change an answer, completely erase the incorrect mark and fill in the correct circle. If you are unsure about how to answer a question, please give the best answer you can.  Today's Date (MM/DD/YY)  Shade circles like this:  Not like this:  Not like this:							
01. In general, would you say your health is:	Excellent	Very Good	Good	Fair	Poor		
The following questions are about activities you might do during a typical day. Does your health now limit you in these activities? If so, how much?	Yes, limited a lot	Yes, limited a little	No, not limited at all				
02. Moderate activities, such as moving a table, pushing a vacuum cleaner, bowling, or playing golf	0	0	0				
03. Climbing several flights of stairs	0	0	0				
During the past 4 weeks , how much of the time have you had any of the following problems with your work or other regular daily activities as a result of your physical health?	All of the time	Most of the time	Some of the time	A little of the time	None of the time		
04. Accomplished less than you would like	0	0	0	0	0		
05. Were limited in the kind of work or other activities	0	0	0	0	0		
During the past 4 weeks , how much of the time have you had any of the following problems with your work or other regular daily activities as a result of any emotional problems (such as feeling depressed or anxious)?	All of the time	Most of the time	Some of the time	A little of the time	None of the time		
06. Accomplished less than you would like	0	0	0	0	0		
07. Did work or activities less carefully than usual	0	0	0	0	0		
08. During the past 4 weeks , how much did pain interfere with your normal work (including both work outside the home and housework)?	Not at all	A little bit	Moderately	Quite a bit	Extremely		
These questions are about how you feel and how things have been with you during the past 4 weeks . For each question, please give the one answer that comes closest to the way you have been feeling. How much of the time during the past 4 weeks	All of the time	Most of the time	Some of the time	A little of the time	None of the time		
09. Have you felt calm and peaceful	0	0	0	0	0		
10. Did you have a lot of energy	0	0	0	0	0		
11. Have you felt downhearted and depressed	0	0	0	0	0		
12. During the past 4 weeks , how much of the time has your physical health or emotional problems interfered with your social activities (like visiting friends, relatives, etc.)?	0	0	0	0	0		
© 1994, 2002 by QualityMetric Inc. and Medical Outcomes Trust. All Rights Reserved. SF-12® is a registered trademark of Medical Outcomes Trust.	15 of 1-			56	8129		

IND 154671

Fipaxalparant (HZN-825)
Protocol: HZNP-HZN-825-303
Version 5.0, Amendment 4

# 17.8 Serious Adverse Events Anticipated in the Trial Population

The following is a list of SAEs by organ system that the Sponsor considers to be associated with the disease state being studied. Please note some of the listed events may need to present with severe intensity to meet the seriousness criteria (e.g., nausea and vomiting). The list does NOT change the reporting obligations or prevent the need to report an AE meeting the definition of an SAE as detailed in Section 9.5.5.1.1.2 (Serious Adverse Event Definition). The Investigator is required to follow the requirements detailed in Section 9.5.5.1.5 (Reporting and Documentation of Serious Adverse Events).

For IND safety reporting, single occurrences of the following events may be excluded from expedited reporting to the FDA. If aggregate analysis of these events indicates they occur more frequently with trial drug compared with placebo, an expedited IND safety report may be submitted to the FDA.

# Cardiovascular system:

- cardiac failure (including acute, chronic and congestive)
- ventricular failure (including ejection fraction decreased)
- pericardial effusion
- pericarditis
- supraventricular tachyarrhythmia
- hypotension

# Pulmonary system:

- pulmonary arterial hypertension
- pulmonary hypertension
- FVC decreased
- respiratory-related hospitalizations
- acute exacerbations

# 17.9 Orthostatic Hypotension Assessment Manual

HZNP-HZN-825-301

Orthostatic Hypotension Assessment Manual

### Orthostatic Hypotension Assessment Manual

## Safety Vital Signs (Supine and Orthostatic) Per Protocol

Information about the orthostatic hypotension assessment and its intended use:

- This assessment is purposed to inform whether treatment with HZN-825 is associated with orthostatic hypotension. This assessment is part of the overall safety evaluation of the current protocol.
- 2. This data is being collected as part of the overall safety analysis for the current trial.

The supine and orthostatic vital signs, as outlined in the protocol along with safety assessments, will be performed using either a standard manual or automated blood pressure cuff. A single measurement will be captured at each of the timepoints as indicated in the protocol and reviewed accordingly. For this assessment, heart rate and systolic and diastolic blood pressure will be measured after 5 minutes in supine resting position followed by measurement after 1 minute and 3 minutes in the standing position.

Positive orthostatic hypotension test is defined as the combination of a reduction of systolic blood pressure by  $\geq 20$  mmHg or reduction of diastolic blood pressure by  $\geq 10$  mmHg, and the presence of one or more of the following associated clinical symptoms:

 lightheadedness, blurred vision, weakness, fatigue, cognitive impairment, nausea, palpitations, tremulousness, headache, presyncope or syncope

If positive for orthostatic hypotension, as defined above (inclusive of clinical symptoms), the subject should be assisted to lie back down in the supine position and monitored for clinical resolution of symptoms.

Prior to beginning the procedure, patients should be instructed to report any symptoms experienced throughout the assessment without probing for specific types of adverse events. If any symptoms occur during the assessment in combination with the blood pressure reductions noted above, they are considered as part of the orthostatic hypotension event and will not be recorded separately as individual adverse events.

If above symptoms are reported by the patient throughout the assessment, without the blood pressure reductions noted above, then the symptoms will only be recorded separately as adverse events if they meet any of the criteria below, and orthostatic hypotension will not be recorded.

- The symptoms are severe and/or require medical interventions
- The symptoms triggered by the OH assessment maneuver and persist for a significantly longer duration beyond the OH assessment period

Version 3.0, Dated 14 June 2023

Page 1 of 3

HZNP-HZN-825-301

Orthostatic Hypotension Assessment Manual

· The symptoms are assessed not due to the maneuver of OH assessment

## Lying Supine and Standing Pulse and Blood Pressure Test (See diagram 1)

#### A. Lying Supine

- Subject should lay supine for approximately 5 minutes (+/- 1 minute), while practicing quiet breathing.
- At the end of approximately 5 minutes (+/- 1 minute), the heart rate and blood pressure will be measured.
- Both assessments of heart rate and blood pressure (including systolic and diastolic) will be collected.
- B. Subject stands upright One Minute Assessment upon standing
  - 1. The subject should change positions from supine to standing.
  - Blood pressure and heart rate will be measured after the subject has been standing for 1
    minute.
  - 3. Both assessments of heart rate and blood pressure will be collected.
- C. Subject remains standing upright Three-Minute Assessment after the subject has stood up
  - Blood pressure and heart rate will be measured after the subject has been standing for 3
    minutes.
  - 2. Both assessments of heart rate and blood pressure will be collected.

The symptoms i.e. lightheadedness, blurred vision, weakness, fatigue, cognitive impairment, nausea, palpitations, tremulousness, headache, presyncope or syncope are reported by the patient throughout the OH assessment, without the blood pressure reductions (reduction in systolic BP  $\geq$  20 mmHg or diastolic BP  $\geq$ 10mmHg), then these symptoms will be recorded as adverse events. Please note that the above-mentioned reported symptoms during OH assessment should only be reported as adverse events separately if they meet any of the below criteria:

- The symptoms are severe and/or require medical interventions
- The symptoms were triggered by the OH assessment maneuver and persist for a significantly longer duration beyond the OH assessment period
- The symptoms are assessed not due to the maneuver of OH assessment

If these symptoms are reported in combination with the blood pressure reductions i.e. reduction in systolic BP  $\geq$  20 mmHg or diastolic BP  $\geq$  10 mmHg, these symptoms will be considered part of the orthostatic hypotension event and will not be reported separately.

Version 3.0, Dated 14 June 2023

[figure not shown]
Page 2 of 3

Fipaxalparant (HZN-825)
Protocol: HZNP-HZN-825-303
Version 5.0, Amendment 4

HZNP-HZN-825-301

Orthostatic Hypotension Assessment Manual

Diagram 1 - Lying Supine and Standing Pulse and Blood Pressure Steps

Record all measurements on CRF

# 17.10 Clinical SAE Report Form

Clinical SAE Report Form for HZNP-HZN-825-303 Version Date: 25 April 2024

### **SAE Report Form Completion Instruction**

Complete the form by filling in the grey boxes electronically (by either double click and select 'checked' or double click and entering a text), printing out, signing and then fax or scan and email immediately and no later than 24 hours of awareness to:

Email (worldwide): [contact] [contact] (toll-free, within USA) [contact] (for non-USA)

If you must fax or email an SAE report form, you must also enter that event into the EDC system when it becomes available

Instructions are not provided for fields that are self-explanatory. Suggestion: Save electronic form with Trial details for future use.

### Enter all dates in the format DD-MMM-YYYY (e.g., 01-Jan-2020)

Date of this report	To be filled out by the investigator. Enter the date the form is being filled out					
Protocol Number	Enter HZNP-HZN-825-303					
Country	Country where the event occurred					
Site Number	Enter number assigned to your site.					
Subject Number	Enter the unique subject code or reference number specific for the trial.					
Type of Report	Choose from the following:  Initial Report					
	
 
If this is the first notification of the serious adverse event (SAE)/adverse event of special interest (AESI).
 
					
	Follow up Report					
	- If this is not the first notification of the SAE/AESI.					
	A follow up report is necessary if there was information missing					
	from initial report(e.g., stop date, outcome was ongoing, patient details, seriousness etc.), further information has been requested,					
	there were errors to be corrected, or the initial report lacked a signature.					
Age at Event Onset	Enter age in years at time of the event occurred.					
Ethnicity	Tick appropriate box for ethnicity.					
Race	Tick appropriate box for race.					

FORM-510389, Effective Date: 25 Apr 2024, Version:1.0

Legacy # FOR-PHV-0001 Page 1 of 11

Fipaxalparant (HZN-825) Protocol: HZNP-HZN-825-303 Version 5.0, Amendment 4

## Clinical SAE Report Form for HZNP-HZN-825-303 Version Date: 25 April 2024

Pregnant	If yes, enter the approximate week of pregnancy and also fill out the corresponding Clinical Trial Drug Exposure During Conception/ Pregnancy report form (Formerly Horizon Legacy Form#: FOR-PHV- 0002, Amgen # FORM- 510390).
Is this event an adverse event of special interest (AESI)?	Check Yes or No (refer to protocol for details)
Date of first awareness of SAE/AESI by the site	Enter the date the first member of the investigator's trial team became aware of the SAE/AESI.
Reported event term	Enter the event term (a medical diagnosis whenever possible). The reporter may be the patient, caregiver, or health care provider, etc.
Start date of the adverse event	This is the date when the event started, which is not the date when the trial team was first aware or informed of the event.  Enter (dd-mmm-yyyy)
Start time of the adverse event	Time when the adverse event started. (Enter time based on 24-hour clock i.e. 1300)
Date when the event became serious	This is the date when the event met one of the following seriousness criteria:
	Results in Death Life threatening Requires inpatient or prolonged hospitalization Persistent or significant disability Congenital anomaly/birth defect Other medically important event (see seriousness criteria below)
Stop date of the adverse event	Date the adverse event stopped. Enter (dd-mmm-yyyy)
Stop time of the adverse event	Time the adverse event stopped. (Enter time based on 24-hour clock i.e. 1300)
Seriousness Criteria	Tick as many of the criteria as apply. However, at least one of the criteria below must be ticked for an adverse event to qualify as serious.  Results in Death (death date: dd-mmm-yyyy)  Life-threatening (places the subject at immediate risk of death from the reaction as it occurred, or it is suspected that the use or continued use of the product would result in the patient's death)  Persistent or significant disability/incapacity (A substantial disruption of a person's ability to conduct normal life functions)  Requires inpatient or prolonged hospitalization (Admission to the hospital for longer than 24 hours or prolongation of a hospital stay due to adverse event; admission and discharge dates: dd-mmm-yyyy)  Congenital anomaly/Birth defect

FORM-510389, Effective Date: 25 Apr 2024, Version:1.0

Legacy # FOR-PHV-0001

Page 2 of 11

Fipaxalparant (HZN-825) Protocol: HZNP-HZN-825-303 Version 5.0, Amendment 4

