# 9.5.5.1.1.2 Serious Adverse Event Definition

A TEAE, baseline event or suspected adverse reaction is considered serious if, in the view of either the Investigator or Sponsor, it results in any of the following:

- Death. This includes any death that occurs during the conduct of a clinical trial, including deaths that appear to be completely unrelated to the trial drug (e.g., car accidents).
- Life-threatening adverse experience. An AE or suspected adverse reaction is considered life-threatening if, in the view of either the Investigator or the Sponsor, its occurrence places the subject at immediate risk of death. It does not include an AE or suspected adverse reaction that, had it occurred in a more severe form, might have caused death.
- Persistent or significant disability or incapacity.
- Inpatient hospitalization or prolongation of an existing hospitalization.
- Congenital anomaly or birth defect.
- Other medically important event that, according to appropriate medical judgment, may require medical or surgical intervention to prevent one of the outcomes listed above.

Surgical procedures or other therapeutic interventions themselves are not AEs, but the condition for which the surgery/intervention is required is an AE and should be documented accordingly.

Elective surgeries that require hospitalization and treatment received at an emergency room or similar facility will not be considered as SAEs unless one of the definitions of an SAE listed above is met.

In addition, hospitalizations for planned procedures are not considered an AE, unless they are prolonged hospitalizations and emergency room visits <24 hours in duration are not considered hospitalizations.

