# 9.5.5.1.3 Intensity or Severity of Adverse Events

All AEs, both serious and non-serious, will be assessed for severity using the Rheumatology Common Toxicity Criteria v2.0 [Woodworth et al., 2007]. The scale displays Grades 1 through 4 with unique clinical descriptions of severity for each AE (including abnormal laboratory values) based on this general guideline.

- Grade 1 (mild) asymptomatic or transient, short duration (<1 week), no change in lifestyle, no medication or over-the-counter drugs
- Grade 2 (moderate) symptomatic, duration 1 to 2 weeks, alter lifestyle occasionally, medications give relief (may be prescription), trial drug continued

Fipaxalparant (HZN-825)
Protocol: HZNP-HZN-825-303
Version 5.0, Amendment 4

- Grade 3 (severe) prolonged symptoms, reversible, major functional impairment, prescription medications/partial relief, hospitalized <24 hours, temporary trial drug discontinuation or/and dose reduced
- Grade 4 (includes life-threatening) at risk of death, substantial disability, especially if permanent, hospitalized >24 hours, permanent trial drug discontinuation

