7.1.4. Serious Adverse Events

Serious adverse events (SAEs) will be identified and captured as SAEs if the AEs met the definitions of SAEs that were specified in the trial protocol. SAEs captured and stored in the clinical database will be reconciled with the Horizon Global Safety database before data finalization.

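### The SAE Report Form's instructions count an admission as serious only if it exceeds 24 hours; the protocol definition sets no minimum stay, so short unplanned admissions may be missed or reported late

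*Protocol*

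**What the plan says.** Protocol 9.5.5.1.1.2 lists, among the outcomes that make an event serious, "Inpatient hospitalization or prolongation of an existing hospitalization". No length of stay is attached. The only 24-hour rule in that section concerns emergency care: "emergency room visits <24 hours in duration are not considered hospitalizations". A second exclusion covers planned admissions: "hospitalizations for planned procedures are not considered an AE, unless they are prolonged hospitalizations". Elective surgery requiring hospitalisation is likewise not an SAE unless one of the listed outcomes is met.

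The completion instructions in Protocol 17.10, under Seriousness Criteria, give the same criterion a narrower meaning: "Requires inpatient or prolonged hospitalization (Admission to the hospital for longer than 24 hours or prolongation of a hospital stay due to adverse event". The same row states that "at least one of the criteria below must be ticked for an adverse event to qualify as serious".

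On the analysis side, SAP 7.1.4 captures events as SAEs "if the AEs met the definitions of SAEs that were specified in the trial protocol" and reconciles the clinical database with the safety database before data finalisation.

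**The concern.** Two current texts in the same protocol give different answers for the same event. A site that reads the form's instruction literally would leave the hospitalisation box unticked for a short admission. If no other box applied, it would conclude that the event is not serious.

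Three things depend on that decision:

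- **Reporting time.** Protocol 9.5.5.1.5 requires SAEs to reach the sponsor within 24 hours of awareness. A site that judges the event non-serious has no reason to start that clock.
- **SAE tabulations.** SAP 7.1.5.1 summarises serious TEAEs by treatment group. The count would depend partly on which text each site applied.
- **Capture of the event at all.** Protocol 9.5.5.1.1.1 has events that are unequivocally disease progression reported as AEs only if they meet an SAE criterion or lead to discontinuation of trial drug. A short admission for IPF progression that is judged non-serious under the form could then go unrecorded even as an AE.

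**Working it through.** No arithmetic applies. The check is to classify the same event under each text.

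| Event, meeting no other seriousness criterion | Protocol 9.5.5.1.1.2 | Form instruction, 17.10 |
|---|---|---|
| Unplanned inpatient stay of more than 24 hours | Serious | Serious |
| Unplanned inpatient stay of 24 hours or less | Serious | Criterion not met |
| Prolongation of an existing stay due to the event | Serious | Serious |
| Emergency room visit under 24 hours | Not a hospitalisation | Criterion not met |
| Planned-procedure stay, not prolonged | Not an AE | Not an AE, so no form is due |

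The texts part company only in the second row. Take an unplanned inpatient stay of 18 hours as an example:

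1. It is an inpatient hospitalisation, so it falls within the protocol's criterion.
2. It is neither an emergency room visit nor a planned procedure, so neither exclusion removes it.
3. Under the protocol it is an SAE.
4. The form asks for more than 24 hours, and 18 hours does not satisfy that. No stay has been prolonged either.
5. With no other box to tick, the form's rule that at least one must be ticked makes the event non-serious.

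Next, whether another passage resolves the conflict:

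- Protocol 17.2 uses a stay of more than 24 hours, but to define hospitalisation due to respiratory distress, an efficacy endpoint. It does not define an SAE, and that endpoint is not affected here.
- Protocol 9.5.5.1.3 describes Grade 3 partly as "prescription medications/partial relief, hospitalized <24 hours, temporary trial drug discontinuation or/and dose reduced". Stays shorter than 24 hours are therefore within what the severity scale contemplates, but the scale does not decide seriousness.
- SAP 7.1.4 points to the protocol definition. That settles which text governs the analysis, but it cannot recover an event that a site never submitted.

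Finally, how far the form reaches. Protocol 9.5.5.1.5 makes eCRF entry the primary route and the form the route when the eCRF cannot be accessed or has been taken off-line. Protocol 9.5.5.1.2 also requires details of all SAEs on the SAE Reporting Form. The form is therefore in regular use, although it is not the only place where seriousness is judged.

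**The case against.** The best case for leaving the form alone is that its parenthesis has little practical force:

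- The duty to report comes from the protocol definition and 9.5.5.1.5, not from completion notes.
- The tick box on the form's data page carries no threshold; it asks for admission and discharge dates. The row for the date on which the event became serious has none either.
- The category for other medically important events remains open and would catch some short stays.
- An event sent by form must also be entered in the EDC system, and the databases are reconciled.
- The Grade 3 wording is generic scale text. The form itself warns against confusing severity with seriousness, so that wording is weak evidence about inpatient admissions.

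Most of this stands, and it limits the consequence. A reader might infer that sites using the form will fail to report short admissions. The documents do not support that: they show a route by which this may happen, alongside other routes by which the event can still be reported.

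A reader might also try to size the problem by applying an assumed rate of short admissions to all 135 subjects. No rate is given. The relevant count is narrower still: unplanned stays of 24 hours or less, with no other criterion met, that a site did not report because of the parenthesis. The form is Version 1.0, effective 25 April 2024, and entered the protocol as an appendix with Amendment 4. The wording of any predecessor is not shown, so its effect cannot be assumed to run through the whole trial.

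The objection does not remove the contradiction. Completion instructions exist to tell a site what a box means, and these tell it something different from the protocol. The residual category depends on judgement and does not automatically catch every short admission.

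**Conclusion.** The point holds as a contradiction between the form's completion instructions and the protocol's SAE definition. It affects one class of event: unplanned inpatient stays of 24 hours or less with no other seriousness criterion met. For that class, SAEs may be missed or reported late by sites that rely on the form. How many cannot be estimated from the documents.

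It would be too strong to say that the protocol makes every hospitalisation serious, because planned-procedure stays that are not prolonged and emergency room visits under 24 hours are excluded. The conclusion assumes that at least some sites consult the instructions when judging seriousness. It would weaken if the eCRF, whose wording is not shown, applies the protocol definition without a time limit, and strengthen if the eCRF repeats the 24-hour limit. No efficacy result is affected.

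**What to change.** 1. Reconcile the two texts by aligning the form's parenthesis with Protocol 9.5.5.1.1.2: inpatient admission or prolongation of an existing stay, without a minimum duration. Keep the exclusion of emergency room visits under 24 hours and the exclusion of planned procedures, including its exception for prolonged stays. The form is the text to change because SAP 7.1.4 already makes the protocol definition govern.
2. Confirm that the seriousness wording in the eCRF matches.
3. Send sites a clarification memo and ask them to check recorded admissions of 24 hours or less against the protocol definition.
4. Leave the 24-hour threshold in Protocol 17.2 as it is; it serves a different purpose.

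The cost is one form revision, a memo to about 85 sites with a limited check of recorded admissions, and possibly a few late SAE reports. No change to the SAP is needed.
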